### **7.1 Visit windows**

For the statistical analyses, data will be analyzed by their target date and time.

### **7.2 Missing Data**

Missing values will not be imputed by estimated values, but treated as missing in the statistical evaluation. All data from all subjects dosed in the study will be included in all listings, plots, summary tables, and statistical analyses when appropriate.

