## **4.3 Sample Size and Power Analysis**

The planned sample size was 120 male patients. Assuming the response rate (the proportion of patients maintaining castrate levels of T ( $T < 50$  ng/dL)) for the placebo group was 5%, the response rate for the low dose group of BHR-200 was 50%, the response rate for the mid dose group was 80%, and the response rate for the high dose group of BHR-200 was 95%, 30 patients per treatment group provided at least 90% power to detect the difference in proportion of patients maintaining castrate levels of T ( $T < 50$  ng/dL) between any dose of BHR-200-treated patients and the placebo-treated patients using a two-sided Fisher-Exact test with a 5% significance level.

However, this study was discontinued prematurely by the sponsor. A final total of 34 study subjects will be included in the analyses.

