## 5 ANALYSIS ENDPOINTS

### 5.1 Efficacy Endpoints

#### Primary Efficacy Endpoint:

The primary efficacy endpoint is the response rate (the proportion of patients maintaining castrate levels of T ( $T < 50$  ng/dL)). The primary analysis on the primary efficacy endpoint is to compare the response rate from each of the 3 BHR-200 dose levels against the response rate for the placebo-treated patients at Week 12.

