## 6 ANALYSIS POPULATIONS

### 6.1 Intent-to-treat (ITT) population

The Intent-to-treat (ITT) population will contain all patients who are randomized into the study. All efficacy parameters will be analyzed using the ITT population. In the case of a patient who was randomized but did not take the study drug, the analysis will be done for this patient using the randomized treatment.

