### **7.3 Post-baseline repeated or unscheduled data**

Repeated or unscheduled data post study drug administration will not be used for data analysis, except for summary tables of the numbers of subjects with notable values of vital signs, physical examination data, and ECG data. All repeated or unscheduled data will be reported in data listings.

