## **11 EFFICACY**

Since the study was stopped prematurely, no planned inferential efficacy analyses will be performed for all of the efficacy parameters. However, the all efficacy endpoints including primary, secondary and exploratory parameters (e.g., FSH, LH, SHBG, and PSA) will be summarized by treatment group at each study visit using descriptive statistics. Serum levels of estradiol and estrone will also be summarized by treatment group at each study visit using descriptive statistics. The Expanded Prostate Cancer Index Composite (EPIC)-Hormonal Assessment and the EPIC-Sexual Assessment will be summarized by treatment group at each study visit using descriptive statistics.

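### The SAP does not say that a man with T ≥50 ng/dL before Week 12 stays a non-responder, or what the denominator of the response rate is

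*SAP*

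**What the plan says.** **Protocol.** The synopsis counts a man as maintaining suppression only if no T measurement in Weeks 4–12 reaches 50 ng/dL (Weeks 4–24 for the secondary endpoint). T is scheduled every 2 weeks, so the primary window holds five visits: Weeks 4, 6, 8, 10 and 12. Section 4.3 lists T ≥50 from Week 4 on as a treatment failure that ends participation. Section 8.5 leaves the handling of missing efficacy data to the SAP.

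**SAP.**
- Section 5.1 describes the endpoint as the proportion maintaining T <50 and omits the Weeks 4–12 window. The primary analysis is "to compare the response rate from each of the 3 BHR-200 dose levels against the response rate for the placebo-treated patients at Week 12".
- Section 11 says "no planned inferential efficacy analyses will be performed for all of the efficacy parameters", and that all efficacy endpoints, the primary included, "will be summarized by treatment group at each study visit using descriptive statistics".
- Section 6.1: "All efficacy parameters will be analyzed using the ITT population". That set is all randomized men. Section 4.3 adds: "A final total of 34 study subjects will be included in the analyses".
- Section 7.2: "Missing values will not be imputed by estimated values, but treated as missing in the statistical evaluation". Its next sentence refers to men dosed, not men randomized: "All data from all subjects dosed in the study will be included in all listings, plots, summary tables, and statistical analyses when appropriate".
- Section 7.3: "Repeated or unscheduled data post study drug administration will not be used for data analysis". The only exception is for tables of notable vital signs, physical examination and ECG values.
- The Kaplan-Meier event in section 5.1 is T >50, as in Protocol 8.7. The protocol synopsis uses T ≥50.

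**The concern.** A man withdrawn for T ≥50 at Week 4, 6 or 8 may contribute no Week 12 measurement. If the response rate is built visit by visit from available values, and absent values are simply missing, he leaves both numerator and denominator. The Week 12 figure then describes men who had not yet failed, which is not the protocol's endpoint. No SAP sentence rules this out, so two programmers could follow the SAP and report different primary rates from the same data.

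Men who leave without a T ≥50 are not settled either: PSA-rise stops, other dropouts, missed visits, men never dosed, and men cut off when the sponsor closed the study.

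With no inferential analysis, this descriptive rate is the main efficacy result, and choosing a Phase 3 dose is still listed as the secondary objective (SAP 3.2).

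**Working it through.** **1. The plan's own figure.** SAP 4.3 claims at least 90% power for each dose against placebo, with 30 per arm, a two-sided Fisher exact test at 5%, and response rates of 5/50/80/95%. Full enumeration gives 98.2% (low) and above 99.9% (mid and high). The claim reproduces. It treats each rate as a proportion of all 30 men in an arm.

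**2. Effect of dropping earlier T failures.** Let p be the response rate over all randomized men, and f the share of failures with no Week 12 value. The rate among the men left is p / [1 − f(1 − p)], which is at least p. The documents give neither failure timing nor laboratory turnaround, so f is an assumption, and the rates are planning values, not results.

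| Assumption | Placebo | Low | Mid | High | High − low |
|---|---|---|---|---|---|
| All randomized (f = 0) | 5% | 50% | 80% | 95% | 45 points |
| Half of failures lack a Week 12 value (f = 0.5) | 9.5% | 66.7% | 88.9% | 97.4% | 30.8 |
| Equal per-visit risk, Week 10 failures still sampled at Week 12: p^(2/5) | 30.2% | 75.8% | 91.5% | 98.0% | 22.2 |
| Equal per-visit risk, no Week 12 value for any earlier failure: p^(1/5) | 54.9% | 87.1% | 95.6% | 99.0% | 11.9 |

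If timing differs by arm, the contrast can widen instead. With f = 0.8 in the high arm and 0 in the low arm, high is 0.95/(1 − 0.8 × 0.05) = 0.990, and 0.990 − 0.500 = 49 points.

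**3. Effect of dropping men who left with every T below 50.** Take 8 men: 4 responders seen at Week 12, 3 failures seen at Week 12, and 1 PSA-rise stop with all T <50. On the T-only wording of the endpoint he is arguably a responder, giving 5/8 = 62.5%. Treated as missing he drops out, giving 4/7 = 57.1%. This lowers the rate.

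**4. Scale of this trial.** 34/4 = 8.5, so 8 or 9 men per arm if the split was even (an assumption). With 8 men and 4 responders, and e of the 4 failures lacking a Week 12 value, the rate is 4/(8 − e): 50, 57, 67, 80 or 100% for e = 0 to 4. One man of unknown status moves an arm by 1/9 = 11 to 1/8 = 12.5 points.

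**5. Two stated rules set against the endpoint.** The endpoint covers any T measurement, but SAP 7.3 keeps an unscheduled value out of the analysis even if it is ≥50. The endpoint fails a man at exactly 50, but the SAP Kaplan-Meier event does not; this matters only for a value of exactly 50.

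**The case against.** The intended meaning is fairly clear. Maintaining suppression is a cumulative idea. Protocol 8.7 uses the same Week 12 shorthand for an endpoint that the synopsis defines over Weeks 4–12. An observed T ≥50 is not a missing value, and Protocol 4.3 calls it treatment failure. The ITT set is all randomized men. SAP precedence under Protocol 8.1 covers inconsistencies with the analyses in that section, so SAP silence does not displace the synopsis definition. SAP 7 also requires tables to show the numbers of subjects and to separate unknown from missing, with all data listed. A rate among men not yet failed could therefore be seen for what it is.

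Most of this stands, and it limits the point. A reader might infer that the SAP requires a rate among men not yet failed. It does not; it leaves that reading open. What the defense does not supply is a rule. The ITT set says who is analyzed, not how a man without a Week 12 value counts, and visible counts do not fix the denominator in advance. The synopsis does not settle men who leave with every T below 50. For a PSA-rise stop the documents pull both ways: the endpoint concerns T only, while Protocol 4.3 labels the stop a treatment failure.

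The unscheduled-value conflict may never arise, since the protocol schedules no repeat T, but a protocol that counts any measurement should not meet a SAP that discards some.

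**Conclusion.** The omission is real. The SAP does not carry over the protocol's cumulative definition, gives no denominator, and contains two rules (SAP 7.3 and the T >50 event) that depart from the endpoint as defined.

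Its effect cannot be sized from the documents. The shift from 5/50/80/95% to about 55/87/96/99% rests on planning rates, equal per-visit risk and no Week 12 value for any earlier failure. The 50% to 100% spread rests on an assumed arm of 8 with 4 responders.

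A reader might infer that reported rates can only be too high, or that dose differences must shrink. Neither follows. Dropping T failures cannot lower an arm's rate and generally raises it, but dropping men who left with all T <50 can lower it, and dose contrasts can move either way with the timing of failures.

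No error rate is at stake, because no test is run. The consequence is a descriptive primary result in 34 men that could be reported in more than one way. It is worth fixing, at the low end of that category.

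**What to change.** **In SAP 5.1, 7.2 and 11:**
- Define response as no T ≥50 ng/dL at any scheduled or unscheduled measurement in Weeks 4–12 (Weeks 4–24 for the secondary endpoint), with all randomized men as the denominator.
- Count an observed T ≥50 in the window as non-response at that visit and every later one. Exempt this endpoint from SAP 7.3.
- Keep men of unknown status in the denominator and show them in their own row: PSA-rise stops, other dropouts, men never dosed, missed visits inside the window, and sponsor closure. Give a range from all counted as non-responders to all counted as responders.
- Set the Kaplan-Meier event to T ≥50, and report Kaplan-Meier suppression probabilities at Weeks 12 and 24 beside the rates.

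**Two sets of passages to reconcile separately:**
- The protocol synopsis and SAP 4.1 end dosing at T ≥50 with no time limit, whereas Protocol 3.0 and 4.3 apply this after 4 weeks. A man stopped on a Week 2 value falls outside the endpoint window and is unclassified. Once the passages agree, the SAP should say how he counts.
- Protocol 3.0 has T assessed through the End of Study visit, whereas Protocol 7.22 and Appendix 1 list no T at End of Study or Early Termination.

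**Cost.** SAP wording and a little derived-dataset programming; no new data. Rates may come out lower than under the by-visit reading, and with 8 or 9 men per arm the unknown-status range may be wide.

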### **7.3 Post-baseline repeated or unscheduled data**

Repeated or unscheduled data post study drug administration will not be used for data analysis, except for summary tables of the numbers of subjects with notable values of vital signs, physical examination data, and ECG data. All repeated or unscheduled data will be reported in data listings.

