Primary	To evaluate the safety and efficacy of three different doses of BHR-200 (0.36% transdermal estradiol gel) compared to placebo for the maintenance of testosterone (T) suppression in men with advanced androgen-sensitive prostate cancer.
Secondary	To select the dose(s) for a subsequent Phase 3 trial.
Study Endpoints	
Primary	Maintenance of T suppression, defined as the absence of any T level measurement greater than or equal to 50 ng/dL during Weeks 4 to 12 of double blind treatment.
Secondary	Maintenance of T suppression, defined as the absence of any T level greater than or equal to 50 ng/dL during Weeks 4-24 of double blind treatment. Incidence and severity of adverse events with special attention given to thromboembolic events. Serum concentrations of: follicle-stimulating hormone (FSH), luteinizing hormone (LH), sex hormone binding globulin (SHBG), and prostate-specific antigen (PSA).
Study Design	
Methodology	This is a multi-center, randomized, double-blind, placebo-controlled, dose-finding study in men with advanced androgen-sensitive prostate cancer. Patients who give informed consent will have screening evaluations, and if fulfilling the entry criteria, will be randomized to one of 4 treatment groups: 1 mL, 2mL or 3mL of 0.36% BHR-200 (transdermal estradiol gel) or placebo. Study drug will be initiated on the day (+/- 5 days) they would be scheduled to receive the next GnRH agonist depot injection. Patients will be offered low-dose radiation to aid in the prevention of gynecomastia. Patients will apply the study drug once per day. The first dose will be applied under the supervision of the PI/designee. Subsequent doses will be self-administered daily by the patient until one of the following occurs:

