4.3 Early Withdrawal of Patients

A patient is free to withdraw from the study at any time for any reason without prejudice to their future medical care by the physician or at the institution. The Investigator or Sponsor may also withdraw the patient at any time in the interest of patient safety. The primary reason for withdrawal must be recorded in the patient's medical record and on the withdrawal form in the Case Report Form (CRF). If a patient is withdrawn for more than one reason, each reason should be documented in the source document and the most medically significant reason should be entered on the CRF. The withdrawal of a patient from the study should be discussed where possible with the Medical Monitor before the patient stops administration of the study drug. If the study drug is discontinued, the final evaluations will be performed as completely as possible. Any comments (spontaneous or elicited) or complaints made by the patient and the reason for termination, date of stopping study drug and the total amount of study drug administered must be recorded in the CRF and source documents.

The following are reasons to terminate the participation of a patient in the study:

- The patient is no longer chemically castrated, after 4 weeks of double-blind treatment or anytime thereafter, indicated by a measurement of T \geq 50 ng/dL. (*treatment failure*)
- The patient's PSA rises >0.5 ng/mL above the baseline measurement (*treatment failure*)
- Lost to follow-up: patient fails to return to the study site for scheduled visits and does not respond to multiple telephone or written attempts to contact (these attempts should be documented).
- Withdrawal of consent: patient decides to stop participation in the study for any reason or is unable to complete the study as described in the study protocol. Although a patient is not obliged to give his/her reason for withdrawing prematurely, the Investigator will make a reasonable effort to obtain the reason while fully respecting the patient's rights. Every effort will be made to contact a patient who fails to attend any follow-up appointments/contacts in order to complete study assessments.
- Administrative: the Sponsor decides to terminate or discontinue the study (either at the study site or the entire study).

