8.0 Statistical Plan

8.1 Statistical Analysis Plan

A statistical analysis plan (SAP) will be written and finalized prior to any lock of the study database. The SAP will give a detailed description of the summaries and statistical methodologies for analyses that will be performed and clearly describe when these analyses will take place. Should any inconsistencies exist between the analyses described in this section and the analyses described in the more detailed SAP, the SAP will take precedence.

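### SAP 7.3 excludes repeat and unscheduled testosterone results from analysis, although the protocol counts any T of 50 ng/dL or more as failure; the SAP should say which T results decide responder status.

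*SAP*

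**What the plan says.** **The SAP rule.** SAP 7.3: "Repeated or unscheduled data post study drug administration will not be used for data analysis". The exceptions are tables counting subjects with notable vital-sign, physical-examination or ECG findings. Everything else, T included, goes to listings only.

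**The protocol endpoints.** The synopsis defines the primary endpoint as the "absence of any T level measurement greater than or equal to 50 ng/dL during Weeks 4 to 12 of double blind treatment" and the secondary endpoint as the "absence of any T level greater than or equal to 50 ng/dL during Weeks 4-24 of double blind treatment". Protocol 4.3 lists as a treatment failure that ends participation: "The patient is no longer chemically castrated, after 4 weeks of double-blind treatment or anytime thereafter, indicated by a measurement of T" at or above 50 ng/dL.

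**The restated endpoint.** SAP 5.1 says: "The primary efficacy endpoint is the response rate (the proportion of patients maintaining castrate levels of T" below 50 ng/dL, compared at Week 12. Protocol 8.7 words it in almost the same way. Both leave out the any-measurement condition and the Weeks 4-12 window.

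**Neighbouring rules.** SAP 7.1: "For the statistical analyses, data will be analyzed by their target date and time". SAP 7.2 leaves missing values as missing and adds: "All data from all subjects dosed in the study will be included in all listings, plots, summary tables, and statistical analyses when appropriate". SAP 8 tabulates reasons for non-completion. SAP 11 drops all inferential efficacy analysis but still summarises the primary and secondary endpoints. Where the protocol's statistical section is inconsistent with "the analyses described in the more detailed SAP, the SAP will take precedence".

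**The concern.** An endpoint that fails on any single high value depends on which values are admitted. The protocol sets no restriction, while the SAP removes a class of values by a general convention that does not mention T. The values removed could include the one on which a man was withdrawn.

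Two tables in one report could then disagree about the same man. The disposition table would give loss of castration as his reason for stopping. The response table would show him as a responder or as missing, and his event could disappear from the Kaplan-Meier summaries. Response rates by dose are the main efficacy result left in a trial that stopped at 34 men, and the secondary objective is dose selection for Phase 3.

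**Working it through.** **1. The plan's own figure.** Protocol 8.2 claims at least 90% power for each dose against placebo: 30 per arm, two-sided Fisher exact test at 5%, response rates 5%, 50%, 80% and 95%. Exact enumeration gives 98.2% for 5% against 50%, and more than 99.9% for 5% against 80% and against 95%. The claim reproduces, and this point leaves it untouched.

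**2. How often T is scheduled.** The schedule in Protocol Appendix 1 gives:
- Weeks 4, 6, 8, 10, 12: 5 samples in the primary window.
- Weeks 4 to 24 every 2 weeks: (24 - 4)/2 + 1 = 11 samples in the secondary window.

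No repeat or confirmatory T is planned.

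**3. One man traced through the rules.** Suppose his scheduled T values are below 50 ng/dL at Weeks 4 and 6, and an extra draw before Week 8 is 50 or more.

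| Rule | His status |
|---|---|
| Protocol synopsis, primary endpoint | Non-responder |
| Protocol 4.3 | Treatment failure, participation ends |
| SAP 8 disposition table | Non-completer, with that reason |
| SAP 7.3 with 5.1, judged on remaining values | Responder |
| SAP 7.3 with 5.1 and 7.2, Week 12 value required | Missing |
| SAP 5.1 time to T event | Event not in the analysed data |

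SAP 7.1 does not rescue the value. It places data by target date but gives no window that would assign an extra sample to a visit. A late scheduled visit is a different matter and is not at issue. SAP 7.2 admits all data only where appropriate and does not say how that fits with 7.3.

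**4. Size for one man.** SAP 4.3 gives 34 men and no split by arm. Assuming roughly equal arms, 34/4 = 8.5, so n is 8 or 9. Let x be the arm's responders among the other men.
- Counted as a responder: the change is 1/n. 1/9 = 11.1 points; 1/8 = 12.5 points. At the planned 30 per arm it would be 1/30 = 3.3 points.
- Missing and removed from the denominator: the change is x/(n-1) - x/n = x/(n(n-1)). At n = 9 this runs from 0 (x = 0) to 8/72 = 11.1 points (x = 8). At n = 8 it runs from 0 to 7/56 = 12.5 points (x = 7).
- Missing but kept in the denominator: the rate stays x/n, with no change.

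**5. The direction is not fixed.** If a man's only in-window T is an extra sample below 50 ng/dL, he is a responder with it and missing without it. Here x includes him, and the rate goes from x/n to (x-1)/(n-1). For example, 7/9 = 77.8% becomes 6/8 = 75.0%, a fall of 2.8 points.

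**6. Threshold.** The responder definition fails a man at 50 ng/dL or more. The synopsis statistical methods use the same threshold for time to event. Protocol 8.7 and SAP 5.1 use strictly above 50. A value of exactly 50 would make a non-responder with no event.

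**The case against.** The strongest reply is that the trigger is hypothetical. T is drawn every 2 weeks, one high value is enough for withdrawal, and no confirmatory draw is called for, so the deciding value will normally be a scheduled one. That stands: the documents do not show that any such sample exists.

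Second, the SAP did not invent the looser wording. Protocol 8.7 also drops the any-measurement condition and the window, and the SAP has precedence on analyses. This is fair as to origin. But the precedence clause compares the SAP with the protocol's statistical section, whereas the endpoint is defined in the synopsis. The SAP nowhere says that it changes the endpoint, so a deliberate redefinition cannot be inferred.

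Third, scheduled-only analysis is defensible, because men with extra draws have more chances to show a high value. That is a real cost of counting every result. It does not remove the clash with an endpoint worded as any measurement.

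Fourth, the excluded values are listed and withdrawal reasons are tabulated, so a careful reader could trace a discordant man. True, but the summary rate would still carry the wrong status.

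A reader might also infer that the exclusion must inflate response rates, or that it biases the comparison of active dose with placebo. The documents support neither. Step 5 of the working shows a fall, and nothing says how extra samples would be spread over the arms.

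**Conclusion.** The conflict is real on the current text. SAP 7.3, taken literally, can contradict the protocol's primary and secondary endpoints and its treatment-failure rule, and no other available SAP text resolves it. This is more than missing detail, because a stated rule could give a man the wrong status on the primary endpoint.

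The size is conditional. One man counted as a responder moves an arm's rate by 11.1 to 12.5 points, assuming 34 men in arms of 8 or 9. That leverage reflects small arms and would apply to any single reclassification. The number of affected men is not given and may be zero. Efficacy is descriptive only under SAP 11, so no p-value or error rate changes. The effect is confined to the response-rate and time-to-T summaries. The correction should be made, but it is not a threat to the trial as a whole.

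**What to change.** Amend SAP 7.3 and 5.1 together:

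1. By-visit descriptive tables use scheduled samples only.
2. Responder status and time to T failure use all post-dose T results, whether scheduled, repeat or unscheduled, within the protocol windows. SAP 5.1 should restate those windows as Weeks 4-12 and Weeks 4-24, because it currently gives none.
3. Reconcile the time-to-event threshold (at least 50 in the synopsis, above 50 in Protocol 8.7 and SAP 5.1) with the responder threshold, and state the result explicitly.

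The cost is a short amendment to two SAP sections and one derivation flag. The values are already to be listed under SAP 7.3, so no new data are needed. The downside is unequal ascertainment in men with extra draws. An optional scheduled-samples-only summary beside the main response rate would show whether it matters.

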6.0 Study Evaluations

6.1 Laboratory Tests

Laboratory tests will be performed by a central laboratory. The following test results will be reported to the Investigator: hematology, blood chemistry, urinalysis, coagulation factors, hormones (including total Testosterone), and PSA. The Investigator will assess all abnormal lab values for clinical significance; if categorized as adverse events, they will be collected and recorded similarly to other AEs. All clinically significant abnormal lab values will be followed until resolution. If resolution is not seen, a justification as to the cause for such an abnormality, such as due to an underlying pre-existing condition, associated co-morbidity, etc., will be recorded.

The following laboratory assessments will be performed for this study.

Hematology:	Hematocrit, Hemoglobin, WBC with differential, RBC, Platelets
Blood Chemistry:	Alanine transaminase (ALT), Albumin, Alkaline phosphatase (ALP), Aspartate aminotransferase (AST), Blood urea nitrogen (BUN), Calcium, Carbon dioxide, Chloride, total Cholesterol, Cholesterol HDL, Cholesterol LDL, Creatinine, Direct bilirubin, Glucose, Lactate dehydrogenase (LDH), Potassium, Sodium, total Bilirubin, total Protein, Triglycerides
Coagulation Factors:	Protein C-activity and antigen, Protein S-activity, Protein S-antigen, Antithrombin III antigen, and Activated protein C resistance (APCR)
Endocrine:	Glycated hemoglobin (HbA1C)
Hormones:	Follicle stimulating hormone (FSH), Luteinizing hormone (LH), and Sex hormone-binding globulin (SHBG)
Urinalysis:	Appearance, Color, Glucose, Ketones, Microscopic, Nitrites, Occult blood, pH, Protein, Specific Gravity
Biomarkers:	
Bone:	C-telopeptide crosslink of type 1 collagen (CTX) – bone resorption

Alkaline Phosphatase, Bone Specific (BSAP) – bone formation

Prostate: Prostate specific antigen (PSA)

Efficacy: total Testosterone

Pharmacokinetic: Estradiol, Estrone

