### **12.2 Vital Signs**

Vital sign parameters include systolic and diastolic blood pressure, body weight, height, BMI, respiration rate, temperature, and heart rate. Vital sign values and changes from baseline in these parameters will be presented using descriptive summaries by visit.

A shift from baseline analysis of abnormalities (normal, abnormal/clinically significant, and abnormal/ not clinically significant) will also be presented by counts and percentages at each post-administration visit and in an overall view regardless of post-administration assessment time point. In addition, at each time point, the sums of subjects with normal, abnormal CS, and abnormal NCS values at that time point will be summarized. Also, at each time point the sums of subjects with normal, abnormal CS, and abnormal NCS values at baseline and values at that time point will be summarized.

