## 12.6 Clinical Laboratory Parameters

Shift analysis (High/Normal/Low), compared to the baseline result, at each visit and an overall view regardless of post-administration assessment time point, and descriptive statistics for the central laboratory values and changes from baseline at each visit will be presented by treatment group, for laboratory parameters collected in the study that include:

Hematology: Hematocrit, Hemoglobin, WBC with differential, RBC, Platelets

Blood Chemistry: Alanine transaminase (ALT), Albumin, Alkaline phosphatase (ALP), Aspartate aminotransferase (AST), Blood urea nitrogen (BUN), Calcium, Carbon dioxide, Chloride, total Cholesterol, HDL Cholesterol, LDL Cholesterol, Creatinine, Direct bilirubin, Glucose, Lactate dehydrogenase (LDH), Potassium, Sodium, total Bilirubin, total Protein, Triglycerides

Coagulation Factors: Protein C-activity and antigen, Protein S-activity, Protein S-antigen, Antithrombin III antigen, and Activated protein C resistance (APCR)

Endocrine: Glycated hemoglobin (HbA1C)

Hormones: Follicle stimulating hormone (FSH), Luteinizing hormone (LH), and Sex hormone-binding globulin (SHBG)

Urinalysis: Appearance, Color, Glucose, Ketones, Microscopic, Nitrites, Occult blood, pH, Protein, Specific Gravity

Biomarkers:

- Bone: C-telopeptide crosslink of type 1 collagen (CTX) – a marker of bone resorption; Alkaline Phosphatase, Bone Specific (BSAP) – a marker of bone formation
- Prostate: Prostate specific antigen (PSA)

Pharmacokinetic: Estradiol, Estrone (no shift analysis will be performed for Estradiol and Estrone data).

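### SAP 7.3 keeps unscheduled laboratory results out of every SAP 12.6 table, including the overall shift, and its exception for notable values is undefined and tied to no table in SAP 12.2 to 12.4

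*SAP*

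**What the plan says.** SAP 7.3 sets the general rule: "Repeated or unscheduled data post study drug administration will not be used for data analysis". One exception follows: "except for summary tables of the numbers of subjects with notable values of vital signs", physical examination and ECG. It closes with a safeguard: "All repeated or unscheduled data will be reported in data listings". Laboratory tests are not named in the exception.

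SAP 12.2, 12.3 and 12.4 cover the three data types that are named. Each plans counts of men who are normal, abnormal and clinically significant, or abnormal and not clinically significant, at each time point. Each also plans a shift from baseline, presented by visit and (in the words of 12.2) "in an overall view regardless of post-administration assessment time point". None of them uses the word notable.

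SAP 12.6 plans a High/Normal/Low laboratory shift "at each visit and an overall view regardless of post-administration assessment time point", with descriptive statistics by visit. The list of parameters includes the coagulation factors.

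Protocol 6.1 adds a follow-up duty: "All clinically significant abnormal lab values will be followed until resolution".

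**The concern.** An overall shift table exists to answer one question: did this man have an abnormal value at any time after dosing? If it draws only on scheduled samples, it answers a narrower question than its description suggests. Unscheduled samples are often taken because something prompted them, so leaving them out can make the laboratory shift look better than the data.

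The coagulation panel is where this matters most. The Protocol synopsis gives special attention to cardiovascular and thromboembolic events and lists coagulation factors among the safety measures. Because SAP 11 drops all inferential efficacy analysis, descriptive tables are the main output of this study.

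The second problem is that the SAP leaves the programmer to guess which tables the exception covers.

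**Working it through.** The SAP states no figure on this point, so the check sets the passages side by side and then gives a scale.

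**1. Do unscheduled laboratory results enter SAP 12.6?** No. SAP 7.3 excludes them and its exception covers only vital signs, physical examination and ECG. The sentence in SAP 7.2, "All data from all subjects dosed in the study will be included in all listings, plots, summary tables, and statistical analyses when appropriate", does not clearly override this: it is general, it is qualified at its end, and the specific rule comes directly after it.

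**2. Which tables does the exception cover?** The counts of abnormal findings in SAP 12.2 to 12.4 concern the same three data types and are plausibly what was meant. But nothing equates notable with either class of abnormality, and no cross-reference exists. Two programmers could reasonably differ on whether an unscheduled ECG enters the overall view. The text of SAP 5.2 (Safety Endpoints) was not available, so a definition there cannot be excluded. It would not be expected to add laboratory tests to the list in 7.3.

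**3. How wide are the gaps between scheduled samples?** From Protocol Sections 7.3 to 7.22 and Appendix 1:

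| Data | Scheduled after baseline |
|---|---|
| Chemistry, hematology, urinalysis | Weeks 12, 24, 36, 48; final visit if previously abnormal or not done in the last 4 weeks |
| Coagulation factors | Weeks 12, 24, 36, 48; none at the final or early termination visit |
| Vital signs | Every visit: 2-weekly to Week 24, then 4-weekly, and the final visit |

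A man who leaves before Week 12 thus has no scheduled post-dose coagulation result. Such departures are expected: Protocol 4.3 ends participation for testosterone at or above 50 ng/dL from Week 4, and Protocol 8.2 assumes that only 5% of placebo patients maintain castrate levels. How many would leave before the Week 12 panel is not stated.

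**4. Which abnormal laboratory values are lost from the overall shift?**

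- A repeat in the same direction as a scheduled post-dose abnormal value: nothing lost, because the man is already counted and the shift carries no grades.
- First abnormal at an unscheduled draw and still abnormal, in the same direction, at a later scheduled draw: nothing lost from the overall view.
- First abnormal in that direction at an unscheduled draw and not seen at any later scheduled draw: lost from SAP 12.6. It reaches a table only if recorded as an adverse event or under a diagnosis; otherwise it is in listings alone.

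**5. Scale.** The SAP gives 34 men in total (Sections 2 and 4.3) and no arm sizes. An equal split would be 34/4 = 8.5. Assuming 7 to 10 per arm, one omitted man changes the arm's percentage by 100/n:

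- n = 7: 14.3 points
- n = 8: 12.5 points
- n = 9: 11.1 points
- n = 10: 10.0 points

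**The case against.** The strongest reply is that little is hidden. Protocol 6.1 and 9.2.2 allow clinically significant laboratory changes to be recorded as adverse events or under their diagnosis. Protocol 6.2 and 6.3 do the same for ECG and physical findings that meet the definition. SAP 12.5 tabulates adverse events without restriction to scheduled visits, and every unscheduled result is listed. This stands, and it defeats the tempting reading that abnormal values drawn for cause reach no safety table. It does not close the gap: recording depends on judgment, adverse event tables show no High/Low shift, and listings give no counts per arm.

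A reader might also infer that the exception has nothing to apply to, so that vital-sign and ECG abnormalities are understated as well. The documents do not support that. The abnormality counts in SAP 12.2 to 12.4 may well be the intended tables, and vital signs are scheduled far more often than every 12 weeks.

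The follow-up duty in Protocol 6.1 mostly generates repeats of abnormalities already found, and many of those change nothing in the shift. It does not show that the most abnormal results are the ones omitted. This stands too.

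The overall view can also be read as pooling scheduled visits only, so there is no outright contradiction with SAP 7.3. Restricting to scheduled samples has a merit as well: it gives men more equal chances of showing an abnormal value. That supports scheduled-only by-visit tables, but is a weaker argument for a table meant to disregard time point.

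**Conclusion.** The concern holds in a limited form. Followed as written, SAP 7.3 stops the overall laboratory shift from counting a value seen as abnormal only at an unscheduled draw, and the any-time laboratory shift can be understated as a result. For vital signs, physical examination and ECG the defect is a missing definition and cross-reference, not a shown loss of data.

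The size of any understatement is unknown, because the documents do not say how many unscheduled samples exist. The 10 to 14 points per man rests on the assumed 7 to 10 men per arm and on one man being omitted; no omitted man has been shown. No adverse event summary changes. The case for acting is that the correction is cheap and makes the table match its description.

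**What to change.** Amend SAP 7.3 and Section 12 as follows.

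- By-visit tables use scheduled results only.
- The overall views in 12.2, 12.3, 12.4 and 12.6 include repeated and unscheduled post-dose results.
- For laboratory tests, a man counts as High if any post-dose value is High and as Low if any is Low. He may count in both, so a footnote should say that percentages can exceed 100. He counts as Normal only if neither applies.
- For vital signs, ECG and physical examination, he is placed in his worst post-dose category: abnormal and clinically significant, then abnormal and not clinically significant, then normal.
- Replace the reference to notable values in 7.3 with a reference to these tables.
- Report the number of men with unscheduled samples in each arm.

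The cost is SAP wording and a program change. No new data are needed, since unscheduled results are already to be listed. If the tables have been run, the added output can be labelled as unplanned, as SAP Section 2 provides. The one downside is that men sampled more often have more chances to show an abnormal value; the per-arm count of men with unscheduled samples is there to make that visible.
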